10.4.6 Follow-up

The study intervention will last 8 weeks (approximately 30 rTMS sessions). The research team will conduct follow-up assessments at the end of treatment and at weeks 12 and 16 post-randomization. There will be flexibility in exact timing of the follow-up assessments in order to accommodate participants’ schedules and to allow for either in-person or electronic communication (e.g., phone or other HIPAA compliant mechanism). In the event that follow-up visits are conducted remotely, the UDS will not be performed.

10.4.7 Referral for Participants Needing Continued Treatment

At the end of study participation (the last follow-up visit), if a participant requires or requests continuing treatment for CUD and/or MUD (as well as other SUDs), an appropriate treatment referral will be made.

10.5 End of Treatment Assessment and 12- And 16-Week Post- Randomization Follow-Up Assessments

Follow-up assessments are expected to be conducted at the end of treatment, and at 12- and 16-weeks post randomization and will be conducted by research staff. Printed reminders for the follow-up assessments will be given to the study participant during the end of treatment

assessment appointment. In addition, research staff will send a reminder in the mail/text/email/or social media (based on study participant preference) about 7 days prior to the scheduled follow-up with an additional reminder notification via mail/text/email/or social media (based on study participant preference) the day before the scheduled follow-up. The end of treatment visit may occur on the day of the last treatment in week 8, or up to 1 week later. Week 12 and 16 follow-up visits may occur no more than 1 week prior to the visit or 2 weeks after the scheduled visit. See Section 12 for assessments to be completed.

10.6 Collection of Biospecimens

Urine samples will be collected from all participants for urine drug screen (UDS), the main efficacy outcome measure of the study. This will occur at screening, randomization, during each treatment session prior to beginning the intervention, during the end of treatment visit and follow-up assessments (UDS will be omitted if follow-up visits are performed remotely). A newly positive UDS will result in recalibration of the motor threshold before rTMS delivery. For females of child-bearing potential, a urine pregnancy test will be administered. Results of the urine pregnancy test will be obtained prior to performing the UDS, at screening, randomization, at weeks 4 and 8 of treatment and at any other time a woman reports she might be pregnant. A positive pregnancy test post-randomization will result in the cessation of rTMS/sham treatment. The research staff will follow the participant until an outcome of the pregnancy is known and reported.

10.7 Premature Withdrawal of Participants

All participants will be followed for the duration of their participation in the study unless they withdraw consent, die, or the investigator or sponsor decides to discontinue their enrollment for any reason. Reasons for the investigator or sponsor terminating a participant from the study may include, but are not limited to, the participant becoming a threat to self or others, the participant acquiring an exclusionary condition, lack of funding, or Data and Safety Monitoring Board (DSMB) early termination of the study for safety reasons.

Should participants be lost to follow-up, efforts to pursue participant locator information such as multiple contact options (e.g., phone, address, email, social media) and collateral contact information will be maintained. At any time, participants may decide that they no longer wish to continue to participate in the study.

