Given the preliminary nature of this study (to better isolate the potential effects of rTMS from the effects of psychosocial substance abuse treatment), participants will not be engaged in formal substance abuse treatment. Participation in self-help groups is allowed. Recruitment will therefore focus on individuals who are willing to try to decrease their cocaine and/or methamphetamine use, but are not engaged or plan to be engaged in formal SUD treatment. If an individual is engaged in formal treatment at the time of recruitment, but chooses to participate in the trial rather than continue treatment, no "wash-out" period will be required. Efforts will be made to advertise and recruit in local communities specifically for individuals interested in decreasing or stopping cocaine and/or methamphetamine use. It is anticipated that enrolled participants will only receive study-related interventions and will not concurrently receive treatment as usual from the sites. However, if an enrolled individual decides to pursue formal treatment and remain in the study, data on time in treatment will be collected. Considering the rigorous time requirements of the rTMS protocol and the fact that we will be providing CBT modules for participant use, we do not anticipate that this will be an issue.

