10.4.3 Safety Monitoring of Intervention

Intervention tolerability and effects will be systematically assessed before and after each treatment. This includes assessing for factors that impact seizure threshold (e.g., increased stimulant use). Retesting of MT may occur as outlined in the rTMS intervention section below. Participants will be encouraged to contact research staff between visits to address any immediate concerns regarding adverse events and medication changes; however, information on adverse events and medication changes also will be collected during assessment and intervention appointments. The Study Medical Clinician will meet with the participant before, during, or after any study intervention if the rTMS Operator or participant is concerned for the potential of a serious adverse event, including seizure. If suspected seizure occurs during study intervention, the Study Medical Clinician will arrange for the participant to be transferred to local emergency

room for further management. In the event of a seizure during the study, the participant will be discontinued from further study intervention.

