10.8 Discontinuing of Study Intervention

Efforts will be made to continue follow-up of participants who discontinue the study intervention, but remain in the study for follow-up.

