- 4) Results in persistent or significant incapacity or substantial disruption of the ability to conduct normal life functions.
- 5) Is a congenital abnormality or birth defect.

- 6) Important medical event that may not result in one of the above outcomes but may jeopardize the health of the study participant or require medical or surgical intervention to prevent one of the outcomes listed in the above definition of serious event.

Definition of Expectedness

Any adverse event is considered “unexpected” if it is not listed in the investigator brochure, package insert or product safety summary or is not listed at the specificity or severity that has been observed. If neither is available, then the protocol and consent are used to determine an unexpected adverse event.

Pregnancy

Any pregnancies that occur while a participant is enrolled in the study will be captured on a pregnancy CRF and not separately reported as an AE or SAE. Women who become pregnant during the active treatment period will be discontinued from further rTMS procedures, referred for medical care, and the pregnancy followed until an outcome is known.

Medical and Psychiatric History

A thorough medical and psychiatric history during the screening phase should record any chronic, acute, or intermittent preexisting or current illnesses, diseases, symptoms, or laboratory signs of the participant, to avoid reporting pre-existing conditions as new AEs and to assist in the assessment of worsening in intensity or severity of these conditions that would indicate an AE. Stable chronic conditions, such as arthritis, which are present prior to clinical trial entry and do not worsen are not considered AEs.

Site’s Role in Eliciting and Reporting Adverse Events

Appropriately qualified and trained personnel will elicit participant reporting of AEs, SAEs and UADEs at each study visit designated to collect AEs. Participants will be asked specifically about common adverse events associated with device use including headaches, device application site pain and hearing changes. Adverse event (medical and/or psychiatric) assessment will initiate with participant consent and follow-up of ongoing adverse events will continue through resolution or 30 days post last study visit. Study personnel will obtain as much information as possible about the reported AE/SAE to complete the AE/SAE forms and will consult with the Safety Monitor/Medical Monitor as warranted.

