The site Medical Clinician must apply his/her clinical judgment to determine whether or not an adverse event is of sufficient severity to require that the participant be withdrawn from further study intervention. The site Medical Clinician should consult with the site Principal Investigator, the Lead Investigator and/or Safety Monitor/Medical Monitor as needed. If necessary, a site Medical Clinician may suspend any trial treatments and institute the necessary medical therapy

to protect a participant from any immediate danger. A participant may also voluntarily withdraw from treatment due to what he/she perceives as an intolerable adverse event or for any other reason. If voluntary withdrawal is requested, the participant will be asked to complete an end of rTMS/sham visit to assure safety and to document outcomes and will be given recommendations for medical care and/or referrals to treatment, as necessary.

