Local Node site visit reports are sent to those entities required of them by the Lead Investigative team, generally including the Lead Investigator, site Principal Investigator, Node PI and a CCC representative, usually the Clinical Study Manager for the study.

E. Management of Risks to Participants Confidentiality

Confidentiality of participant records will be secured by the use of study codes for identifying participants on CRFs, and secure storage of any documents that have participant identifiers on site, as well as secure computing procedures for entering and transferring electronic data. The documents or logs linking the study codes with the study participant on site will be kept locked separately from the study files and the medical records. No identifying information will be disclosed in reports, publications or presentations.

Information Meeting Reporting Requirements

The consent form will specifically state the types of information that are required for reporting and that the information will be reported as required. These include suspected or known sexual or physical abuse of a child or elders, or threatened violence to self and/or others.

Participant Protection

The site's study clinician will evaluate all pertinent screening and randomization assessments prior to participant randomization to ensure that the participant is eligible and safe to enter the study. AEs and concomitant medications will be assessed and documented at each study visit. Individuals who experience an AE that compromises safe participation in a study will be discontinued from further rTMS intervention and provided referrals for other treatment or to specialized care. Study personnel will request that the participant complete an end-of- intervention visit to assure safety and to document end-of-intervention outcomes.

Pregnancy

A positive pregnancy test post-randomization will result in the cessation of rTMS/sham treatment. The research staff will follow the participant until an outcome of the pregnancy is known and reported.

Study Specific Risks

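### SAP Tables 69 and 70 divide suicidal-ideation counts by all randomized in every period, so participants never assessed in a period count as free of ideation

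*Protocol*

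**What the plan says.** Table 69 (SAP 17.1.8) counts participants who endorse any of CHRT-SR items 14 to 16 at least once in screening, the treatment period or follow-up. Rows are split by MDE at baseline and columns by arm. Footnote 3 makes the number randomized the denominator. Table 70 does the same for the clinician-rated CHRT-CR, again over the number randomized.

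The CHRT-SR is scheduled at screening, weekly in treatment, at end of treatment, and at Weeks 12 and 16 (Protocol 12.6.4). The CHRT-CR follows only a positive CHRT-SR (Protocol 12.6.5). In the SAP the follow-up period consists of the Week 12 and Week 16 visits alone (3.2.4). Recording a visit as not attended waives every assessment due at it (Protocol 12.2.4).

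Participants can go unassessed by missing visits or by leaving the study. On leaving, Protocol 10.7 says that reasons for removing someone "from the study may include, but are not limited to, the participant becoming a threat to self or others, the participant acquiring an exclusionary condition". On stopping treatment, Protocol 10.8 says: "Efforts will be made to continue follow-up of participants who discontinue the study intervention, but remain in the study for follow-up".

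For the urine drug screen the SAP works differently. Table 48 uses as its weekly denominator the participants who have a screen that week, and Table 46 shows by arm how many have one.

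**The concern.** For a randomized participant with no CHRT-SR in a period, the trial does not know whether ideation was present. The tables enter that person as a non-event. Absence of information and absence of ideation become the same thing on the page.

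Two consequences follow. The printed percentage is lower than the percentage among those actually asked. And if the arms differ in how many were asked, the printed percentages can differ when the rates among those asked are equal. Suicidal ideation is one of the device-safety events named in Protocol 12.5.1, so a reader will look at these rows for a signal and should be able to see how many people each rate rests on.

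**Working it through.** The plan gives no ideation rate and no assessed count, so there is no plan figure to reproduce. The check is an identity plus illustrations.

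**Inputs from the documents:** 160 planned, allocated 1:1, so 160/2 = 80 per arm; the all-randomized denominator; a 75% target for completing all follow-up visits (Protocol 2.5).

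**Assumed:** a 10% ideation rate, the fractions assessed, and the number lost selectively.

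**1. Identity.** Let N be the number randomized, m the number with at least one CHRT-SR in the period, and x the number endorsing. Then x/N = (x/m) × (m/N): the printed rate is the rate among those assessed times the fraction assessed.

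**2. Dilution.** With N = 80, m = 60, x = 6: the rate among those assessed is 6/60 = 10.0%, and the table prints 6/80 = 7.5%. For other fractions, 10% × 0.90 = 9.0% and 10% × 0.95 = 9.5%.

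The 75% case needs care. If the trial-wide target for completing all follow-up visits is met, at most 0.25 × 160 = 40 participants miss one or more. Some of those will still attend the other visit and be assessed. The target does not bound either arm separately.

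**3. Between arms.** With 10% in both arms among those assessed:
- 60 v 70 of 80 assessed: 6/80 = 7.5% v 7/80 = 8.75%. The gap of 1.25 points is 1/80, one participant.
- 65% v 85% assessed: 10% × 0.65 = 6.5% v 10% × 0.85 = 8.5%, a gap of 2.0 points.

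**4. What the planned outputs recover.** Table 14 gives attendance by arm at Week 12 and at Week 16 separately. From n12 and n16 attended, the number seen at least once lies between max(n12, n16) and min(N, n12 + n16). With 60 and 60 of 80 that is 60 to min(80, 120) = 80, so the same 6 endorsers mean anything from 6/60 = 10.0% to 6/80 = 7.5%. Attendance is tabulated by site, arm and primary substance, not by MDE, so the MDE rows have no counterpart. Listings 5 and 6 cover only participants who endorsed ideation, so they do not give m.

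**5. Selective loss.** Suppose 8 of 80 have ideation (10.0%) and 4 of those 8 are the only ones not assessed. The table prints 4/80 = 5.0%. The assessed denominator gives 4/76 = 5.3%. With a row stating that 4 were not assessed, the reader can bound the rate between 4/80 = 5.0% and (4 + 4)/80 = 10.0%.

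**6. Which rows.** Both footnotes apply to every period, so the treatment-period rows have the same property. With weekly CHRT-SRs, more participants should have at least one there, so the dilution is probably smaller; the documents give no count. Screening rows should be essentially unaffected, since the instrument is part of screening.

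**The case against.** The denominator is a stated convention. The footnotes disclose it, each cell prints the count as well as the percentage, and the AE, SAE, device-reaction and UADE tables also divide by the number randomized. Attendance is a close proxy for CHRT-SR completion: Table 14 reports it by arm, Table 20 gives missed follow-up visits with reasons, and Table 9 gives early terminations by arm, with a row for psychiatric risk. SAP 7.7 lists completion of all follow-up visits as an exploratory measure; if it were reported by arm for the same two visits, the number seen at least once would be n12 + n16 minus the number attending both. Ideation that qualifies as an SAE is reported elsewhere. Table 48 is a weekly efficacy summary rather than an at-least-once safety incidence. The illustrative sizes are assumed.

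Much of this stands, and it keeps the point small. It would be wrong to say that the plan shows nothing about who was seen. What remains is that none of these outputs counts CHRT-SRs or splits by MDE, and the exploratory measure is optional with no table shell. The AE analogy is also imperfect: an AE may be reported spontaneously, whereas a CHRT-SR endorsement exists only if the form was completed.

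A reader might also infer that Protocol 10.7 conflicts with the event-specific stopping rules and so ends follow-up improperly. The seizure rule says "In the event of a seizure during the study, the participant will be discontinued from further study intervention", and the pregnancy and adverse-event rules likewise stop stimulation only (10.6 and Appendices A and B). But 10.7 is permissive, and a general power can sit beside specific rules. Nor do all event rules stop at treatment: the rescue plan in 10.4.5 can remove a participant from the study, and 16.10 suspends research contact on incarceration, subject to an exception. How much discretion to give the investigator is a trade-off, and no error is shown.

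**Conclusion.** The point holds as a minor reporting weakness. In Tables 69 and 70, non-assessment from any cause is counted as no ideation, and the planned tables do not let a reader recover the number assessed by period, arm and MDE group. With an assumed 10% rate, the shortfall is 2.5 points at 75% assessed and 0.5 points at 95%; the 60 v 70 example between arms amounts to one participant. These sizes rest on assumptions, and 80 per arm is the planned figure.

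Two stronger readings go too far. One is that the printed rate necessarily understates the rate in the whole cohort. It is lower than the rate among those assessed, but it falls below the unknown full-cohort rate only if some unassessed participants would have endorsed ideation. The other is that only the follow-up rows are affected; the treatment-period rows share the denominator. The tables are descriptive, no test depends on them, and the primary and secondary outcomes are untouched.

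**What to change.** In the treatment-period and follow-up rows of Tables 69 and 70, use as denominator the participants with at least one CHRT-SR in that period, within arm and MDE group. The CHRT-SR is the right base for Table 70 as well, because the clinician rating is triggered by it. Add a row giving the number randomized but not assessed in the same cells. The all-randomized percentage may be kept alongside.

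The cost is one denominator and one added row per period in two tables, from data already collected, so it can be done after database lock. The drawback is that denominators will differ between periods, so rows are less directly comparable. The assessed denominator removes the dilution but does not repair selective loss; the not-assessed row is what lets a reader bound it.

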10.8 Discontinuing of Study Intervention

Efforts will be made to continue follow-up of participants who discontinue the study intervention, but remain in the study for follow-up.

10.9 Study Pause Rules

The safety and preliminary efficacy of using rTMS to assist those with SUD has been evaluated in several studies (see Rao et al., 2019). Nevertheless, the study DSMB will have access to all adverse events and other reportable events. Should the DSMB (or sponsor) determine that the study should be temporarily suspended or terminated, the Lead Investigators will work with the sIRB of record and each of the participating sites to promptly inform them of the reasons for study termination or temporary suspension and to identify the circumstances in which the study may resume.

The following study stopping rules will automatically pause or halt further enrollment and will trigger a review by the DSMB:

- Two or more participants experience severe (Grade 3) neurological reactions
- One serious, unexpected and related adverse reaction

10.10 Blinding

10.10.1 Type of Blinding

This is a double-blind, sham-controlled study.

10.10.2 Maintenance of Blind

With the exception of specified individuals at the DSC and the safety staff at the CCC, all other study personnel and participants will remain blind to intervention status until completion of the trial at all study sites. A Data and Safety Monitoring Board (DSMB) will review study data. DSMB reports will be blinded, though the blind may be broken in the closed session upon request.

10.10.3 Breaking the Blind

In rare cases, it may be necessary to break the blind for a particular participant before completion of the trial (e.g., pregnancy or other medical necessity). The request to break the blind for an individual participant will be made by study Lead Investigators and/or site Principal Investigator.

Unblinding the participant should only occur in cases of medical emergency when knowledge of the treatment group investigational method may be necessary for clinical management and decision-making. The decision to break the blind for a participant will be made jointly by the CCC Safety/Medical Monitor and at least one of the Lead or site Principal Investigators.

10.11 Participant Remuneration

Because of the expected difficulty of maintaining high follow-up rates in the study population, adequate compensation for time and inconvenience is critical. Compensation will be in accordance with the IRB of record's policies and procedures, subject to IRB approval, and will occur on the following study activities:

- Consent and baseline data collection
- Treatment session attendance
- Daily assessment
- End of treatment assessment
- Week 12 follow-up assessment
- Week 16 follow-up assessment
- Completion of EEG (if available at the study site)
- Returning smart-phone device or to reimburse for data plan usage for those who used their own device

Compensation will occur following each visit with procedures specified in the SOP. Sites may reimburse participants directly for mileage expenses based on procedures specified in site operating procedures (SOPs).

11.0 rTMS INTERVENTION

11.1 Overview

Study participants will be randomized to receive up to 30 sessions of either active rTMS or sham across 8 weeks. Flexible treatment appointments will be offered, with every effort made to schedule participants for 3-5 sessions/week. Stimulation will follow FDA-approved protocol for Major Depressive Disorder: 10 Hz stimulation at 120% of the motor threshold intensity and a total of 3000 pulses per session using a figure-8 coil. We will not restrict sites to using a specific device model, as long as the device is capable of delivering this stimulation protocol with sham treatment above.

